3.3. Revised cut-points for variables used in subgroup analyses

RATIONALE:

The protocol specified cut-points for subgroup analyses based on educated guesses about the distributions of variables. After investigating baseline distributions of age and AER in pooled analyses, we changed the cut-points for these variables to achieve better balance in subgroup sample size: (1) for age from 40 to 50 years (median age 52 years), (2) for iGFR from 70 to 60 ml/min/1.73 m² and (3) for AER from 300 to 30 mg/24h (median AER 42 mg/24h).

PROTOCOL:

To investigate the possible presence of heterogeneity in the response to allopurinol, subgroup analyses (based on the primary efficacy analysis described in section 11.3, with the inclusion of an interaction term of the treatment group by the subgroup variable) will be performed by age groups (≤ 40 and >40 yrs.), ..., baseline iGFR (≤ 70 and >70 ml/ min/1.73m²) ... AER at baseline (≤ 300 and >300 mg/24 hr.), and

SAP:

To investigate the possible presence of heterogeneity in the response to allopurinol, subgroup analyses (based on the primary efficacy analysis described in section 11.3, with the inclusion of an interaction term of the treatment group by the subgroup variable) will be performed by age groups (≤ 50 and >50 yrs.), ..., baseline iGFR (≤ 60 and >60 ml/ min/1.73m²) AER at baseline (≤ 30 and > 30 mg/24 hr.), and

3.4. Calculations of visit windows for the analytical dataset

RATIONALE:

Per-protocol windows for scheduling Visits 6-16 are calculated relative to the Visit 5 date. In early versions of the Study Protocol (versions 5.0 and 6.0), randomization was performed at a study visit (Visit 5) and consequently the visit date and randomization date were equivalent. Starting with Study Protocol, version 7.0, Visit 5 became a phone call visit and randomization did not necessarily occur on the date of the phone call. For analytical purposes (see SAP Section 6.3), visit windows will be calculated relative to randomization date.

PROTOCOL:

Visit 1 will be considered as Time 0 for scheduling Visits 2-5, Visit 5 will be considered as Time 0 for scheduling Visit 6-16, Visit 16 as Time 0 for scheduling Visit 17.

SAP:

Visit 1 will be considered as Time 0 for scheduling Visits 2-5, Visit 5 will be considered as Time 0 for scheduling Visit 6-16, Visit 16 as Time 0 for scheduling Visit 17. For analytical purposes, the randomization date will be considered as Time 0 for calculating windows for Visits 6-16.

3.5. Additional analysis assessing an effect of post-randomization serum uric acid changes on iGFR values at Visit 17

RATIONALE:

Following internal discussion on the importance of the relationship between serum uric acid (sUA) and iGFR measures, we added this analysis.

PROTOCOL:

Not applicable

SAP:

Details are provided in SAP Section 6.8.4.

3.6. Additional analysis assessing treatment effect on time to 40% eGFR decrease

RATIONALE:

Following internal discussion on the importance of the recently proposed measure of kidney decline, namely 40% eGFR decrease, we added this analysis.

PROTOCOL:

Not applicable

SAP:

Details are provided in SAP Section 6.8.5.

3.7. Additional analysis assessing time to doubling of serum creatinine, end-stage renal disease (ESRD), or cardiovascular/renal death

RATIONALE:

Following internal discussion on the importance of the recently proposed measure of kidney decline, namely using cardiovascular/renal death as part of the composite endpoint definition, we added this analysis.

PROTOCOL:

Not applicable

SAP:

Details are provided in SAP Section 6.8.6.

3.8. Modifying definition of per-protocol analysis set

RATIONALE:

Following internal discussion we modified the per-protocol definition as follows.

PROTOCOL:

- **Per Protocol:** ... The per protocol population will exclude subjects ... as well as data points for which the cumulative exposure to the study medication from

randomization to that time point was less than 80% of the theoretical full exposure (see Section 11.1 in the protocol).

SAP:

- **Per Protocol:** ... The per protocol population will exclude subjects ... for whom the average drug exposure was less than 80% (see Section 11.1 in the protocol).

4. Study Aim

The study aim is to determine whether lowering serum UA by means of oral allopurinol is effective in preventing or slowing decline of renal function in T1D patients with history and/or presence of microalbuminuria or moderate macroalbuminuria, or with ongoing GFR loss regardless of history or presence of albuminuria, who have only mildly or moderately impaired kidney function.

5. Study Estimands

This section describes the primary and secondary estimands for corresponding endpoints and variables of interest. We follow ICH-E9 (R1) recommendations and specify estimands in terms of four attributes defining the treatment effect of interest:

- A1. The target population
- A2. The variable (or endpoint) to be obtained for each patient that is required to address scientific question of interest
- A3. Strategies for addressing intercurrent events
- A4. The population summary for the variable (endpoint), that provides a basis for a comparison between treatment conditions.

In Table 5.1. we include various intercurrent events that occurred in the PERL study and divide them into three groups, based on their implications for subsequent data collection of the endpoint of interest.

Table 5.1. Groups of intercurrent (IC) events in PERL study

Group of IC events	IC event	Implications for Post-IC data
Group A	Non-adherence to study drug schedule	Post-IC data are collected, but their interpretation may be affected depending on the estimand of interest
	Permanent discontinuation of study drug	
	Use of prohibited medication	
	Missed scheduled visit	
Group B	ESRD treatment (hemodialysis or transplant for ESRD subjects)	Post-IC data do not contain any relevant information about estimands of interest and for this reason they are not collected
Group C	Early discontinuation from the study	Post-IC data cannot be collected
	Terminal event, i.e. death	

5.1. Primary estimand for iGFR at Visit 17 endpoint

This is the de-facto (effectiveness) estimand of the primary endpoint – iGFR at Visit 17 – that quantifies a treatment effect due to the initially randomized treatments as actually taken, i.e., the treatment of allopurinol versus placebo without a confounding effect of treatment for ESRD subjects. The four attributes of this estimand are as follows:

A1. Target population: Individuals with T1D meeting the inclusion/exclusion criteria specified in the Study Protocol.

A2. The variable (or endpoint): The primary endpoint is the measured glomerular filtration rate (GFR) based on plasma disappearance of non-radioactive iohexol (iGFR) at the end of the 2-month wash-out period (Visit 17 at Week 164) following the 3-year intervention. The rationale of measuring the primary outcome at the end of the wash-out period is to test allopurinol for *durable* effects on the natural history of kidney disease, independent from any transient, hemodynamic effect that the medication may have on GFR. iGFR is calculated from blood samples drawn at baseline and 120, 150, 180, 210, and 240 minutes after an i.v. bolus of iohexol, adjusting for body surface area.

A3. Strategies for different groups of IC events: Depending on IC event group membership (see Table 5.1), the variable of interest, in this case iGFR values, collected after an IC event in

- Group A will be considered as directly interpretable. Effectively, IC events in this group are ignored, which is consistent with the ITT principle.
- Group B are assumed to follow a hypothetical scenario, in which variable of interest after developing ESRD takes on biologically plausible values that are not confounded by IC event i.e. by ESRD treatment.
- Group C are assumed to conform to a hypothetical scenario in which post-IC values of the variable of interest (or endpoint) have a similar distribution to other non-ESRD subjects

A4. Population summary to compare treatments: Population-average treatment effect on iGFR at V17.

5.2. Secondary estimands

5.2.1. Estimand for iGFR at the end of the 3-year treatment period (Visit 16, before the washout) a secondary endpoint

This is de-facto (effectiveness) estimand for the iGFR at Visit 16 endpoint with the following attributes:

A1. Target population: T1D (inclusion/exclusion criteria specified in the Study Protocol)

A2. Variable of interest (endpoint): iGFR calculated at the end of the 3-year intervention (at Visit 16, last visit before washout)

A3. Strategies for different groups of IC events: The same as those used for primary estimand (see Section 5.1)

A4. Population summary to compare treatments: Population-average treatment effect on iGFR at V16

5.2.2. Estimand for iGFR time trajectory estimated from repeated iGFR measurements

This is de-facto (effectiveness) estimand for repeated iGFR measures with the following attributes:

A1. Target population: Individuals with T1D meeting the inclusion/exclusion criteria specified in the Study Protocol.

A2. Variables of interest: Repeated measures of iGFR at Visits 11, 16, 17.

A3. Strategies for different groups of IC events: The same as those used for primary estimand (see Section 5.1)

A4. Population summary to compare treatments: Population-average treatment effect on the slope of iGFR trajectory

5.2.3. Estimand for estimated Glomerular Filtration Rate (eGFR) at 4 months after randomization (Visit 7)

This is de-facto (effectiveness) estimand for eGFR at 4 months after randomization with the following attributes:

A1. Target population: Individuals with T1D meeting the inclusion/exclusion criteria specified in the Study Protocol.

A2. Variable of interest (endpoint): eGFR at 4 months after randomization as estimated from serum creatinine and cystatin C using the CKD-EPI SCr and the CKD-EPI SCr-SCysC equations (Inker et al, 2012, Fan et al, 2015). This endpoint is employed to measure a transient, hemodynamic effect that the study medication may have on GFR.

A3. Strategies for different groups of IC events: The same as those used for primary estimand (see Section 5.1)

A4. Population summary to compare treatments: Population-average treatment effect on eGFR at 4 months after randomization.

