11.4. Secondary Efficacy Analyses

1. The effect of treatment on the iGFR at the end of the 3-year treatment period (before the washout) will be evaluated using the same analytical approach employed for the primary outcome.
2. The effect of treatment on the eGFR at 4 months after randomization will be evaluated using the same analytical approach employed for the primary outcome.
3. The iGFR and eGFR time trajectories, estimated from periodical iGFR measures and quarterly serum creatinine and cystatin C measurements using the CKD-EPI SCr and the CKD-EPI SCr-SCysC equations^{34,35}, respectively, will be analyzed using linear mixed-effects models.⁴⁰⁻⁴² The main objective of the analysis will be to construct confidence interval for the effect of the intervention over three years of observation (treatment main effect) and investigate whether the effect of the intervention changes with time (time by treatment interaction).
4. Time to serum creatinine doubling or ESRD in the two treatment groups is subject to censoring due to dropouts or reaching the end of study before the participant experiences the event. Survival time will be defined as the time from randomization to the event (the first of serum creatinine doubling from baseline or occurrence of ESRD, defined as eGFR \leq 15 ml/min/1.73 m², hemodialysis, or kidney transplant) or, for participants who did not experienced an event, to the last study visit. Data will be summarized by means of Kaplan-Meier survival curves and by providing the proportions of participants surviving without events at 1, 2, 3 years, and at the end of the wash-out period along with their 95% CIs. Given the potentially small number of events, differences between study groups will be tested by means of the log rang test or by means of simple Cox regression models including a limited number of predictors in addition to treatment group.
5. The effect of treatment on the AER at the end of the wash-out period, based on the geometric mean of two AER measured at this time point and adjusted for the geometric mean of AER at baseline (Visit 3 and 4), will be investigated in a linear regression model framework as in the case of the primary outcome.

6. The effect of treatment on the AER at the end of the treatment period, based on the geometric mean of the AER measures at visit 15 and 16 adjusted for the geometric mean of AER at baseline (Visit 3 and 4) will be investigated as in #5.

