5.2.4. Estimand for estimated GFR (eGFR) time trajectory

This is de-facto (effectiveness) estimand for eGFR trajectory with the following attributes:

A1. Target population: Individuals with T1D meeting the inclusion/exclusion criteria specified in the Study Protocol.

A2. Variable of interest (endpoint): Repeated eGFR measures at all post-randomization visits (Visit 6 through 17) as estimated from repeated serum creatinine and cystatin C measurements using the CKD-EPI SCr and the CKD-EPI SCr-SCysC equations.

A3. Strategies for different groups of IC events: The same as those used for primary estimand (see Section 5.1)

A4. Population summary to compare treatments: Population-average treatment effect on the slope of post-randomization eGFR trajectory

5.2.5. Estimand for time to doubling of serum creatinine or end-stage renal disease (ESRD)

This is de-facto (effectiveness) estimand for doubling of serum creatinine or developing ESRD with the following attributes.

A1. Target population: Individuals with T1D meeting the inclusion/exclusion criteria specified in the Study Protocol.

A2. Variable of interest (endpoint): This secondary endpoint is defined as a composite of two events: (1) doubling to serum creatinine, and (2) ESRD. Time to event is defined as time from randomization to the first event (one of the events defined above) or censoring (lost-to-follow-up, withdrawal, death, and study completion without experiencing the event).

A3. Strategies for different groups of IC events: Depending on IC event group membership (see Table 5.1) variable of interest/endpoint values, collected after IC event in

- Group A will be considered as directly interpretable. Effectively IC events in this group are ignored, which is consistent with the ITT principle.

- Groups B and C are assumed to conform a hypothetical scenario in which the variable of interest/endpoint values have a similar distribution to subjects not experiencing the IC event.

A4. Population summary to compare treatments: Hazard ratio for allopurinol versus placebo.

5.2.6. Estimand for urinary AER at the end of the two-month wash-out period (Visit 17)

This is de-facto (effectiveness) estimand for AER at V17 with the following attributes.

A1. Target population: Individuals with T1D meeting the inclusion/exclusion criteria specified in the Study Protocol.

A2. Variable of interest (endpoint): Geometric mean of two urinary AER measures obtained at Visit 17.

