6.7. Analyses for secondary estimands

In this section we present analyses aligned with secondary estimands defined in section 5.2. Analyses will be performed using the multiple imputation technique, except those involving time-to event endpoints (sections 6.7.5, 6.7.8).

6.7.1. iGFR at the end of the 3-year treatment period (Visit 16, before the washout)

In this section we describe the analysis (estimator) aligned with the estimand for iGFR at the end of the 3-year treatment period (Visit 16, before the washout) endpoint defined in Section 5.2.1.

The least square means at Visit 16, estimate of treatment effect *at Visit 16* adjusted for baseline covariates, their 95% confidence interval and P-value will be obtained as part of the primary analysis of the primary estimand (Equation (6.1) in section 6.1.1). In the context of this secondary endpoint, we are interested in the fixed effect β_{12} , which represents the treatment effect at Visit 16 adjusted for stratifying variables and baseline covariates. To assess the hemodynamic/transient effect of the allopurinol, we will estimate the contrast $\beta_{12} - \beta_{13}$ between the treatment effect at Visit 16 (before washout) compared to that at Visit 17 (after washout).

6.7.2. iGFR time trajectory estimated from repeated iGFR measurements

This analysis is aligned with the estimand defined in Section 5.2.2

Estimand	See section. 5.2.2 for definition
Analysis	Analysis of the Secondary Endpoint: iGFR time trajectory estimated from repeated iGFR measurements.
Analysis Set	ITT Population
Methods	Linear mixed-effects model for longitudinal iGFR measures using multiple imputation technique.
Dependent Variable	iGFR measured at Visits V11 (80 weeks) , V16 (156 weeks) and V17 (164 weeks after randomization)
Model	
Fixed effects associated with:
 
 • Stratifying variables: sUA, HbA1c, study center • Treatment group • Time since randomization (in years) associated visit windows defined in section 6.3 • Time by treatment group interaction • Albuminuria status with 2 levels • Baseline AER geometric mean (at Visits 3 and 4 combined) expressed on log to base 10 scale • Baseline iGFR 
Subject-specific random effects
 
 • Random intercept for iGFR • Random slope for iGFR

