Results	
 • iGFR slope estimates and 95%CIs by treatment group • Estimate of a treatment effect measured as a difference between average slopes of iGFR versus time for allopurinol and placebo groups adjusted

	for stratifying variables and baseline covariates 
 • 95% confidence interval for treatment effect • P-value for treatment effect
--	--

6.7.3. eGFR at 4 months after randomization (Visit 7)

Estimand	See section 5.2.3 for definition
Analysis	Analysis of the Secondary Endpoint: eGFR at 4 months after randomization (Visit 7).
Analysis Set	ITT Population
Methods	Linear model using multiple imputation technique.
Dependent Variable	eGFR measured at Visit V7 (16 weeks after randomization)
Model	Fixed effects associated with: 
 • Stratifying variables: sUA, HbA1c, study center • Treatment group • Albuminuria status with 2 levels • Baseline AER geometric mean (at Visits 3 and 4 combined) expressed on log to base 10 scale • Baseline eGFR
Results	
 • Least square eGFR means at Visit 7 by treatment group. • Estimate of treatment effect at Visit 7 adjusted for stratifying variables and baseline covariates • 95% confidence interval for treatment effect • P-value for treatment effect

6.7.4. eGFR time trajectory

Estimand	See section 5.2.4 for definition
Analysis	Analysis of the Secondary Endpoint: eGFR time trajectory estimated from repeated eGFR measurements using multiple imputation technique..
Analysis Set	ITT Population
Methods	Linear mixed-effects model for longitudinal eGFR measures using multiple imputation technique.
Dependent Variable	Post-randomization eGFR measured from Visits V6 through V17
Model	Fixed effects associated with: 
 • Stratifying variables: sUA, HbA1c, study center • Treatment group • Time since randomization in (in years) associated visit windows defined in section 6.3 • Time by treatment group interaction • Albuminuria status with 2 levels • Baseline AER geometric mean (at Visits 3 and 4 combined) expressed on log to base 10 scale • Baseline eGFR Subject-specific random effects 
 • Random intercept for eGFR • Random slope for eGFR

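### The iGFR slope runs one straight line through two on-drug visits and the off-drug washout visit, so any reversible drug effect appears as a slope difference of opposite sign; the eGFR slope shares the flaw to a smaller degree.

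*SAP*

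**What the plan says.** SAP 5.2.2 sets the variable for the iGFR trajectory as "Repeated measures of iGFR at Visits 11, 16, 17" and takes the treatment effect on the slope as the summary. SAP 6.7.2 fits a linear mixed model to those three visits with treatment, "Time since randomization (in years) associated visit windows defined in section 6.3", "Time by treatment group interaction", baseline covariates including baseline iGFR, and a random intercept and slope. It reports the difference in average slopes with a confidence interval and P-value. SAP 5.2.4 and 6.7.4 have the same structure for eGFR, with dependent variable "Post-randomization eGFR measured from Visits V6 through V17". Neither model lists a term for being on or off drug.

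Study drug stops at V16 (Protocol 8.6), and V17 follows an 8-week washout (Protocol 8.7). SAP 5.1 explains that the primary endpoint is placed at V17 so that the result is "independent from any transient, hemodynamic effect that the medication may have on GFR". SAP 5.2.3 uses eGFR at V7 to measure that transient effect. SAP 6.7.1 estimates it again as the V16 treatment effect minus the V17 treatment effect.

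Protocol 11.4, item 3, describes the aim of the trajectory analysis as to "construct confidence interval for the effect of the intervention over three years of observation".

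**The concern.** The plan treats a reversible haemodynamic effect as a real possibility and keeps it out of the primary endpoint, but the slope models have nowhere to put it. In each arm one line passes through on-drug visits and then an off-drug visit at the far end. A constant on-drug offset between arms is absorbed by the treatment main effect. Its disappearance at V17 then tilts the line. No off-drug visit at the start balances V17, because V4 enters only as a covariate.

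A drug that only raised GFR while taken would therefore seem to speed GFR loss, and one that only lowered it would seem to protect. The two slopes are among eight secondary outcomes, each tested at an unadjusted 0.05 (SAP 6), and they bear directly on the stated aim of slowing decline.

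**Working it through.** **Planning figures.** Protocol 11.10 uses a difference of 3, residual SD 10.1, two-sided 0.05 and 80% power. n = 2 × (1.96 + 0.84)² × 10.1² / 3² gives 178 per group, against the stated 180. The same section assumes losses of 3 and 2 ml/min/1.73 m² per year, so the planned slope difference is 1 per year. The slope outcomes have no power calculation of their own.

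**iGFR slope bias.** After multiple imputation every participant has the same three analysis times. The mixed-model slope difference then equals the least-squares slope of the arm difference. This was confirmed by generalised least squares under three sets of variance components. Put the arm difference at V11, V16, V17 as (h, h, 0) and use slope = Σ(t − t̄)y / Σ(t − t̄)², with 52.18 weeks per year.

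- Scheduled weeks 80, 156, 164: mean 133.33; deviations −53.33, 22.67, 30.67; sum of squares 4298.7. Slope = (−53.33 + 22.67)h / 4298.7 × 52.18 = **−0.37h per year**.
- Attributed weeks 80, 164, 174 (SAP Table 6.3.2): mean 139.33; deviations −59.33, 24.67, 34.67; sum of squares 5330.7. Slope = −34.67h / 5330.7 × 52.18 = **−0.34h per year**.

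The size of h is an assumption, taken here as 1 to 3 ml/min/1.73 m² in either direction with full reversal by V17:

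| Size of h | Bias in size, attributed weeks | Bias in size, scheduled weeks |
|---|---|---|
| 1 | 0.34 | 0.37 |
| 2 | 0.68 | 0.74 |
| 3 | 1.02 | 1.12 |

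With h = −3 and no durable effect, the estimated slope difference is about +1.0 to +1.1, the whole planned benefit. With h = +3 and a true benefit of 1, the estimate is −0.02 to −0.12. If only half of h reverses by V17, the bias halves to −0.17h to −0.19h.

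**eGFR slope bias.** There are twelve visits, V6 to V17. V6 is scheduled at week 4, when the 100 mg starting period ends (Protocol 6.1.2), so the effect may be incomplete there. Let f be the share of h present at V6.

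- Attributed weeks: mean 88.5; sum of squares 35,631; V17 lies 85.5 above the mean and V6 83.5 below. Slope = [−85.5 + 83.5(1 − f)]h / 35,631 × 52.18. This is −0.125h for f = 1, −0.064h for f = 0.5 and −0.003h for f = 0.
- Scheduled weeks: mean 86.83; sum of squares 33,155.7; deviations 77.17 and −82.83. The same formula gives −0.121h, −0.056h and +0.009h.

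**Precision of the options.** Assumed: 265 per arm (530/2), random-intercept SD 15, random-slope SD 2.5 per year and residual SD 5. These imply an SD at V17 given baseline of about 10.5, near the planned 10.1. For a post-baseline slope, SE = √[(2/265)(2.5² + 5²/S)], with S the sum of squares of time in years².

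- V11, V16, V17 at scheduled weeks: S = 4298.7/52.18² = 1.58; SE = √[(2/265)(6.25 + 15.83)] = 0.41.
- V11 and V16 only: S = 2888/52.18² = 1.06; SE = √[(2/265)(6.25 + 23.57)] = 0.47; bias zero.
- V4, V11, V16 and V17 as responses, with a common V4 mean, visit effects, treatment × time and treatment × on-drug: generalised least squares gives SE 0.28 and zero bias for a constant on-drug effect.

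Over slope SD 2 to 3 and residual SD 4 to 6, the first figure ranges from 0.33 to 0.49 and the last from 0.22 to 0.33.

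**The case against.** The strongest reply is that the plan already protects its main conclusion. The primary endpoint is at V17. The V16 and V17 effects come from a model with a separate treatment effect at each visit. The V7 eGFR analysis and the V16 minus V17 contrast would place an estimate of the transient effect beside the slopes. This stands, and it is why the point concerns secondary outcomes only. But none of these analyses corrects the slopes, which carry their own intervals and P-values. The model in Protocol 11.7 that adds 4-month GFR as a covariate is exploratory, does not address V17, and is absent from SAP 6.9.

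A second reply is that h may be small or only partly reversed in 8 weeks. This also stands: the bias is proportional to the part reversed, and the documents do not size it.

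Three stronger readings are tempting but unsupported:

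- A reader might infer that the eGFR slope is always biased by −0.12h. That needs the full effect at V6, which closes the 100 mg period. At half effect the bias is about −0.06h, and with none it is negligible.
- A reader might infer that removing the bias itself improves precision. The smaller SE in the four-visit model comes from using V4 as a response. Simply dropping V17 raises the SE.
- A reader might infer that Protocol 11.3 already constrained baseline means to be equal. It used baseline iGFR as a response but states no such constraint.

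**Conclusion.** The point holds for the iGFR slope as specified. Any on-drug effect that reverses by V17 enters the slope difference with opposite sign, at −0.34h to −0.37h per year. That is about 0.3 to 1.1 ml/min/1.73 m² per year in size for an assumed h of 1 to 3 and full reversal, against a planned difference of 1. For eGFR the flaw is the same in kind but at most about a third as large, and it depends on how much of the effect is present at V6. Nothing here shows that allopurinol has such an effect or that the primary result is at risk. The slope analyses should be changed because, as written, they cannot separate a reversible effect from a change in progression.

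**What to change.** **iGFR (SAP 6.7.2, with attribute A2 in 5.2.2 amended to match).** Model iGFR at V4, V11, V16 and V17, with V4 as a response whose mean is common to both arms. Include visit effects, treatment × time, and treatment × on-drug (1 at V11 and V16, 0 at V4 and V17). Report treatment × time as the slope effect. This needs SAP wording and no new data, but it has costs to disclose:

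- It assumes a constant effect while on drug.
- It changes the estimand to a baseline-to-washout slope. Under the assumed variances its estimate correlates about 0.96 with the baseline-adjusted V17 effect, so it adds little independent information to the primary.

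The simpler alternative is V11 and V16 only. It keeps a purely on-drug slope and is also unbiased for a constant on-drug effect, at an SE of about 0.47 instead of 0.41.

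**eGFR (SAP 6.7.4, with attribute A2 in 5.2.4 amended to match).** Exclude V6 and V17 and fit the on-drug slope over V7 to V16, or use the on-drug-term model with V6 left out. Dropping V17 alone is not enough: if the effect is absent at V6, V6 to V16 still carries about +0.14h to +0.15h per year. Do not code V6 as fully on-drug in the on-drug-term model, since that can add up to about +0.10h.
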